3.6.2 Table of Benchmarks

| Feasibility and Acceptability Metric | Benchmark to meet |
|---|-------------------|
| Intervention engagement over 10 weeks | |
| % days of self-monitoring body weight, steps, dietary intake (assessed separately) | 75% |
| % days of self-monitoring eating window* | 75% |
| % days of self-monitoring Red Zone Foods (when instructed to do so)* | 75% |
| % action plans completed; feedback emails read; lessons reviewed (assessed separately)* | 80% |
| Goal attainment over 10-week intervention | |
| % of days meeting the daily calorie goal | 75% |
| % of days meeting the daily step goal | 75% |
| % of days meeting the daily eating window goal | 75% |
| % of days meeting the daily Red Zone Food goal (when instructed to track them) | 75% |
| % of days meeting the daily protein goal* | 75% |
| Recruitment, retention, and survey completion | |
| % enrolled among those eligible from the online screen* | 50% |
| % retention at 4 weeks*, 10 weeks | 80% |
| % survey completion at baseline, 4 weeks*, 10 weeks | 80% |
| Acceptability | |
| % of participants who would recommend the weight loss program to a friend who is trying to lose weight | 80% |
| % of participants who indicated the [] goal was moderately , very , or extremely helpful (separately for all goals: calorie, steps, eating window, Red Zone Foods, protein, 10-week weight loss, weekly weight loss)* | 80% |

| | |
|---|------------------------------|
| % of participants who indicated that tracking [] was moderately, very, or extremely helpful (assessed separately for all self-monitoring domains: weight, food, steps, weight)* | 80% |
| % of participants who indicated that receiving a personalized progress report, lesson, action plan (assessed separately) was moderately, very, or extremely helpful * | 80% |
| Clinically significant weight loss | |
| ≥ 3% weight loss at 10 weeks* | At least 50% of participants |
| ≥ 5% weight loss at 10 weeks* | At least 33% of participants |

* indicates exploratory outcome (not reported on clinicaltrials.gov)

3.7 Data Collection

Data will be collected at baseline, 4 weeks, and 10 weeks. All data collection procedures will occur through remote means. Weights will be collected via e-scale, self-monitoring data will be collected objectively by the digital tools, and all other measures will be collected via online questionnaire (REDCap or a dietary recall tool). Fitabase software will be used to retrieve the objective self-monitoring data via Fitbit's API. At the time of each remote evaluation, participants will be emailed instructions for weighing themselves on their e-scales, and sent a link to the online survey to complete measures. Reminders will be sent if weights are not synced or surveys not completed.

3.7.1 Randomization and Masking

Following recommendations for factorial designs, we will randomize participants to the 16 conditions using permuted block randomization with a block size of 16. The

allocation sequence will be generated by the study's PI and stored in REDCap. Study staff will use REDCap to implement the random allocation sequence (i.e., randomize a participant) once both the baseline weight and web-based surveys are submitted. The first day of the weight loss intervention will occur approximately two days after randomization. On that day, participants will receive an automated email describing their treatment assignment. Participants will not be masked to treatment assignment. Study staff will not be masked to treatment assignment due to logistical limitations and the need for quality assurance. However, all surveys will be sent via REDCap and completed without study staff involvement. In addition, study staff will not have access to the allocation sequence.

3.7.2 Quality Assurance

Participants enrolled in this study may not participate in other research studies where weight loss is targeted. In addition, participants will be asked to refrain from self-monitoring behaviors that are not assigned to them and refrain from using any other weight-related apps or activity trackers for the duration of the trial. By explaining the rationale of the study prior to enrollment and setting expectations upfront, we hope to keep compliance with these instructions high.

3.7.3 Research Ethics Approval

The Stanford Institutional Review Board has approved our study protocol.

3.7.4 Protocol Amendments

Protocol modifications will be communicated to all study investigators and approved by

the IRB prior to implementation, and the trial registry will be updated accordingly.

3.7.5 Declaration of Interests

The investigators report no competing interests.

3.8 Sample Size and Statistical Power

Aligning with recommendations for conducting pilot studies, the purpose of our proposed pilot study is to assess feasibility and acceptability of the intervention. As a result, no power analysis will be conducted. The sample size (n=32) was selected to have the same number of participants (n=2) per condition and allows us to meet budget and time restrictions.

3.9 Statistical Analysis

We will use descriptive data to assess feasibility and acceptability outcomes, and will compare them to our *a priori* feasibility benchmarks, outlined in the **Table** above. To evaluate exploratory changes in efficacy outcomes that will be evaluated in a larger-scale trial, we will descriptively assess the main effects of each goal-setting component being tested, along with their interactions. Unlike in an RCT that compares the means of each treatment arm to one another, a factorial trial compares the means across *combinations of experimental conditions* and uses the entire sample, which makes it an efficient and economical study design. For example, the main effect of the Calorie Goal intensity is calculated by computing the mean for the participants who receive the harder goal (i.e., those in experimental conditions 9-16 in the Table above) versus the mean of those who

receive the easier goal (i.e., those in experimental conditions 1-8), collapsed across the other factors. In a subsequent optimization trial, we will be powered to detect these effects.

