3.5 Experimental Intervention Components

Participants will be randomized to 1 of 16 conditions (**Table above**) that vary in their receipt of harder vs. easier goals across 4 goal domains. A 2^4 full factorial design will allow for all combinations to be tested.

Calorie goal (easier vs. harder). It is common in behavioral obesity treatment to assign a tailored calorie goal based on an individual's baseline height, weight, sex, age, and normal activity level, with a minimum of 1200 Calories (kcal)/day for women and 1500 kcal/day for men, based on national guidelines. In this pilot study, participants will be randomized to receive either an *easier* calorie goal (i.e., the tailored calorie goal plus

250 extra calories in daily budget) or a *harder* calorie goal (i.e., the standard calorie goal as is).

Step goal (easier vs. harder). In the baseline survey, participants will complete the Godin Leisure-Time Exercise Questionnaire that will provide a leisure score index to be used determine their baseline activity level. Scores of 0-13 (interpreted as “Insufficiently Active”) will be assigned a baseline goal of 5,000 steps per day, scores of 14-23 (“Moderately Active”) will be assigned a baseline goal of 7,000 steps per day, and scores ≥ 24 (“Active”) will be assigned a baseline goal of 10,000 steps per day. Participants will be randomized to receive either an *easier* step goal (i.e., this baseline step goal as is) or a harder step goal (i.e., this baseline step goal plus 1,500 steps). Beginning in week 2, this step goal will adapt each week based on the prior week’s progress. Participants will receive a daily step goal of either the 40th (if easier) or 60th (if harder) percentile of the prior week’s daily step count, rounded up to the nearest 500 steps.

Eating window goal (easier vs. harder). Limiting eating windows is the crux of time restricted eating. Participants who receive the easier version of this goal will be instructed to eat within a 12-hour window every day, while those receiving the harder version will be instructed to eat within a 9-hour window every day. Participants will be able to self-select at baseline their preferred eating window (e.g., 9 AM to 9 PM for someone in the easier version, or noon to 9 PM for someone in the harder version).

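### Section 3.9 describes exploratory main effects only as raw collapsed means, which separate the four goals only while the 16 cells stay equal

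*Combined protocol and SAP*

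**What the plan says.** Section 3.9 introduces the factor comparisons with "To evaluate exploratory changes in efficacy outcomes that will be evaluated in a larger-scale trial", and continues: "we will descriptively assess the main effects of each goal-setting component being tested, along with their interactions". The one worked example is the calorie goal. It takes the mean of conditions 9-16 and compares it with the mean of those who "receive the easier goal (i.e., those in experimental conditions 1-8), collapsed across the other factors". For these comparisons the section names no factorial model, covariate, interval or rule for missing outcomes. It gives no estimator for the interactions.

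The design behind this is a 2^4 full factorial (Section 3.5) with "the same number of participants (n=2) per condition" (Section 3.8), allocated by "permuted block randomization with a block size of 16" (Section 3.7.1). On timing, Section 3.7 states: "Data will be collected at baseline, 4 weeks, and 10 weeks". Section 3.6.1 names weight change as an outcome and makes feasibility and acceptability the primary outcomes. Section 3.6.2 sets an 80% benchmark for retention at 10 weeks. No dropout assumption is stated anywhere.

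**The concern.** In a balanced 2^4 design the factor columns are orthogonal, so a difference of collapsed means is a clean main effect. With two people per cell, the first lost participant halves a cell and the second may empty it. Once cells are unequal, people on the harder and easier levels of one goal no longer have the same mix of the other three goals, and the raw difference carries part of those goals' effects. An empty cell also affects the planned interactions, and the plan does not say what happens then.

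The second issue is precision. Baseline values are collected, but Section 3.9 does not use them as covariates. At stake are the exploratory efficacy contrasts, on outcomes that the plan intends to study again in a larger trial.

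**Working it through.** **The plan's own figure.** 2^4 cells × 2 = 32, which agrees with Section 3.8. There is no power figure to reproduce.

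**Balance at entry.** Code each factor -1/+1. With all 32 observed, every cross-product of two factor columns is 0, so the raw collapsed difference equals the estimate from a four-factor main-effects model exactly.

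**Empty cells.** Assumption: 80% retained at random, or about 26 of 32 (range 29 to 22).
- Independent losses: 1 - (1 - 0.2²)^16 = 1 - 0.96^16 = 48%.
- Exactly L lost: 1 - C(16,L)·2^L / C(32,L).
  - L = 6: 1 - 8008·64/906192 = 43%.
  - L = 3: 1 - 560·8/4960 = 10%.
  - L = 10: 1 - 8008·1024/64512240 = 87%.

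**Mixing under random dropout.** Define leakage as the share of another goal's effect that enters the raw contrast. From 10,000 random draws at each size:

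| Retained | Mean leakage | SD per other goal | Largest of three, 95th percentile |
|---|---|---|---|
| 29 | 0 | 0.06 | 0.12 |
| 26 | 0 | 0.09 | 0.23 |
| 22 | 0 | 0.13 | 0.28 |

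This is noise, not bias. Removing it with a main-effects model costs little: at 26 retained, the standard error is 0.399 outcome SDs against 0.394.

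**Mixing under concentrated dropout.** Illustration: 50% retained where the calorie and eating-window goals are both harder, 90% elsewhere. Overall retention is (4·0.5 + 12·0.9)/16 = 0.80.
- Share with the harder window goal, calorie-harder: 0.5/(0.5 + 0.9) = 0.357. Calorie-easier: 0.9/1.8 = 0.500.
- Leakage: 0.357 - 0.500 = -0.143.
- Each effect 2: raw = 2 - 0.143·2 = 1.71. Simulation gives about 1.70; the main-effects model gives 2.00.
- Calorie effect 1, window effect 3: raw = 1 - 0.143·3 = 0.57. Simulation gives 0.55 to 0.58; the model gives 1.00 to 1.03.
- Extreme case, all six losses in one such pair: 2 of 10 calorie-harder completers have the other harder goal, so leakage is 0.20 - 0.50 = -0.30.

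By contrast, retention that falls steadily from 95% with no harder goals to 65% with four gives leakage of only -0.002.

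**When a main-effects model is not enough.** Keep the 50%/90% pattern, but let the calorie effect be 4 with the easier window and 0 with the harder one (average 2), with an average window effect of 2. Let the mean with both goals easier be a.
- Raw: both calorie-harder groups have mean a + 4, and the calorie-easier groups average a + 2, so the contrast is 2.0.
- Main-effects model: it weights the two window levels by 0.9·0.9/1.8 = 0.450 and 0.5·0.9/1.4 = 0.321, giving 4·0.450/0.771 = 2.33 in large samples. Simulation at this sample size gives 2.39 to 2.43.

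Including the calorie-by-window term removes this bias.

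**Baseline as a covariate.** With equal variances and pre-post correlation ρ, the variance of a change score is proportional to 2(1 - ρ), and with baseline adjustment to 1 - ρ². The information ratio is 2/(1 + ρ). The documents give no ρ, so a range is shown.

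| ρ | Information ratio | Gain |
|---|---|---|
| 0.5 | 1.333 | 33% |
| 0.7 | 1.176 | 18% |
| 0.9 | 1.053 | 5% |
| 0.95 | 1.026 | under 3% |

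**The case against.** The strongest reply is that these comparisons are descriptive and exploratory, that the collapsed mean is offered as an example, and that it correctly describes a balanced design. No section says that the estimates will set the size of the later trial or select its components. Section 2.1 makes feasibility and acceptability the condition for going on. All of that stands, and it limits the priority.

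Four stronger readings are tempting and are not supported:

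- **That baseline is ignored.** Section 3.9 speaks of changes, Section 3.6.1 of weight change, and Section 3.6.2 of percentage weight-loss thresholds. Baseline is the reference value; it is only absent as a covariate.
- **That modelling the factors sharpens the estimates greatly.** With residual SD 4, each effect 2 and 80% random retention, the sampling SDs are 1.65 raw, 1.64 with four factors and 1.46 with a baseline covariate correlated 0.5 with the outcome. The last step is worth about 27% more information, (1.64/1.46)² = 1.26 from the rounded values, and rests on that assumed correlation. The factors themselves add almost nothing.
- **That bias should be expected.** The documents predict no dropout pattern, and 80% is a target to meet, not an accepted loss. Random or steadily rising dropout gives essentially no bias. Even in the concentrated illustration, root mean squared error is 1.67 raw against 1.65 with the model, and 1.70 against 1.66 in the case with a window effect of 3.
- **That a main-effects model is always safer.** The interaction example shows otherwise.

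**Conclusion.** The point holds in a limited form. The only estimator described depends on equal cells, and at 80% retention those cells will very probably be unequal, with a 43% to 48% chance that at least one is empty. Material systematic mixing needs dropout concentrated in a particular combination of goals. In the illustration it takes a true 2.0 to about 1.7. That is plausible in a study of harder goals, but it is an assumption.

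The gain from a baseline covariate is likely small for weight if its pre-post correlation is high. It is larger for outcomes with a lower correlation, which may include dietary recall or self-reported activity. The primary feasibility and acceptability results are unaffected, so this is a low-priority improvement.

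**What to change.** In Section 3.9, state that the exploratory factor effects come from one linear model with the four factors effect-coded (-1/+1) and the baseline value of the outcome where one exists. Report the main effects both without and with the six two-way interactions, because the first version can be biased under uneven dropout if goals interact. Give 95% intervals and the observed number in each cell, and state how missing outcomes are handled. Omit three- and four-way terms if any cell is empty.

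The cost is wording. Before the covariate is added, the main effects equal the raw differences if nobody is lost. The price is degrees of freedom: the fuller model has 1 + 4 + 6 + 1 = 12 parameters on about 26 people, so its intervals will be wide. Neither version corrects for dropout that depends on the unobserved outcome, and the report should say so.

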3.10 Data Management

REDCap will be used for direct data entry, randomization, and tracking participants' status in the study.

3.11 Endpoint

The behavioral intervention is 10 weeks in length and will not be terminated early based on efficacy. The study is expected to end after we reach our target sample size and the final participant has completed the intervention.

4. Risks and Protection Against Risks

4.1 Potential Risks

Potential risks include: 1) breach of confidentiality; 2) psychological distress associated with answering questions about psychological or behavioral content (e.g., perceived stress level, weight bias, body weight) or engaging in the intervention; 3) medical risks associated with participating in a behavioral weight loss treatment. These risks are consistent with typical risks associated with research participation in behavioral weight loss studies and are expected to be minimal. There are no invasive procedures planned. We will monitor the occurrence of adverse events and serious adverse events as required for these types of intervention studies.

4.2 Safeguards to Minimize Risks

4.2.1 Participant Population and Screening

All participants will be adults with overweight/obesity who are otherwise healthy.

Individuals who are pregnant or who have a medical condition that would limit participation in a behavioral weight loss intervention or be better suited for a more intensive or different type of intervention are excluded from our trial (e.g., individuals with a history of an eating disorder or cardiovascular event, uncontrolled diabetes mellitus or hypertension, cancer, dementia). Healthy volunteers are included to reduce the risk of any complications that could arise from participation in a behavioral weight loss intervention that is of lower intensity and remotely delivered. Risks to participants are anticipated to be low given that we are examining evidence-based intervention strategies and promoting weight loss through lifestyle change (e.g., decrease intake of unhealthy foods, increase steps). We will not be including a vulnerable population (e.g., children, pregnant women) as participants.

To ensure participant safety in this study, a set of screening procedures that are common in behavioral weight loss interventions, such as ensuring participants are safe to engage in moderate intensity physical activity and ensuring participants do not have a medical condition that is contraindicated in a remote weight loss program will be employed. The content of the weight loss intervention – including moderate-intensity physical activity and dietary change through reduction of unhealthy foods and increase of healthy foods – is commensurate with the current national guidelines for behavioral obesity treatment.

4.2.2 Study Team

The Principal Investigator will be responsible for regular monitoring of data. All study procedures involving participant contact will be done by trained research personnel who have completed formal human subjects training (e.g., CITI Certification) to ensure understanding of methods and procedures to protect personal health information, and the importance of maintaining the confidentiality of study participants.

4.2.3 Adverse Events

Information will be collected on all potential types of adverse events, including musculo-skeletal soreness and injury, as well as major medical events including injuries or conditions that result in health care provider visits or hospitalization. Serious adverse events will be reported promptly in writing to the Stanford IRB, and all adverse events reported to the appropriate entities as required throughout the study.

Participants will be provided with contact information for the study team, including a study phone number and study email address that will be checked daily by the study's Research Assistant (RA) and/or the PI. This contact information will be provided to participants on multiple occasions, including in the informed consent form, in weekly intervention-related emails, and in the study evaluation emails sent at baseline, 4 weeks, and 10 weeks. In addition, participants will speak to study staff via phone/video conference at the beginning of the study (before randomization) to ensure eligibility, interest, and understanding of study procedures and assigned intervention components. During this call, participants will be encouraged to report any adverse events, serious adverse events, or discomforts that arise during the trial to the study team.

The RA will be the primary source of contact with participants (e.g., sending intervention materials and survey measures via email). The RA will alert the PI of any negative participant feedback. Based on participant feedback, the PI will revise the intervention and study procedures as necessary to ensure that risks of injury or discomfort are minimized and will seek IRB approval before doing so. All study personnel will have access to each other's contact information, including an email address and phone number, in a centralized database to facilitate easy communication.

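### The only adverse-event route described after randomization is participant-initiated contact, although surveys already go to everyone at 4 and 10 weeks, so events are likely to be under-counted

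*Combined protocol and SAP*

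**What the plan says.** Section 4.1 (Potential Risks) lists psychological distress and medical risks of weight loss treatment, and states "We will monitor the occurrence of adverse events and serious adverse events as required". It gives no method.

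Section 4.2.3 (Adverse Events) opens with a broad commitment: "Information will be collected on all potential types of adverse events, including musculo-skeletal soreness and injury". It also names events leading to a provider visit or hospitalization. The arrangements it then describes are these:

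- **Contact details.** "Participants will be provided with contact information for the study team, including a study phone number and study email address". These appear in the consent form, in the weekly intervention emails and "in the study evaluation emails sent at baseline, 4 weeks, and 10 weeks". The phone and inbox are checked daily.
- **One call.** The section says that "participants will speak to study staff via phone/video conference at the beginning of the study (before randomization"). On that call, "participants will be encouraged to report any adverse events, serious adverse events, or discomforts that arise during the trial to the study team".
- **Relay.** "The RA will alert the PI of any negative participant feedback". The investigator may then revise the intervention or procedures, with IRB approval, to limit injury or discomfort.

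Sections 3.1 and 3.7 schedule remote assessments at baseline, 4 weeks and 10 weeks, each with a link to an online survey. Section 3.7.1 says surveys go out through REDCap and are completed without staff involvement.

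**The concern.** Each arrangement in section 4.2.3 needs the participant to decide that something is worth reporting and then to make contact. The one described call comes before the intervention starts, so it can invite later reports but cannot elicit an on-treatment event. Serious events may well reach the team this way. Soreness, minor injury and distress are the kind that people often do not write in about, and soreness is named in the commitment.

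The pilot is meant to show whether easier and harder goals are feasible and acceptable before a fully powered trial. Physical and psychological discomfort are plausible costs of a harder goal. If the record holds only volunteered events, a short list cannot be read as good tolerability. The safeguard by which the investigator revises the intervention in response to feedback rests on the same volunteered information. Participants also know their assignment (section 3.7.1), so readiness to report could depend on it.

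**Working it through.** **Step 1. Is a scheduled question described anywhere?** Comparing the sections that would hold one:

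| Section | Content | Adverse-event question described? |
|---|---|---|
| 3.4 Core Intervention | Self-monitoring tools; weekly action-plan survey on behaviors, confidence and barriers | No |
| 3.6.1 Overview of Measures | Weight, dietary recall, physical activity, perceived ease | No |
| 3.6.2 Table of Benchmarks | Engagement, goal attainment, retention, acceptability, weight loss | No |
| 3.7 Data Collection | Weights, self-monitoring data, other measures by online questionnaire | No |
| 3.9 Statistical Analysis | Descriptive benchmarks and main effects | No |
| 4.2.3 Adverse Events | Contact details, one call, relay of feedback | No; the 4- and 10-week emails are mentioned only as carrying contact details |

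**Step 2. Inputs for an illustration.**

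- N = 32, from section 3.8. It reproduces: 16 conditions × 2 = 32.
- Survey completion benchmark 80%, from section 3.6.2: 0.80 × 32 = 25.6, about 26 responders.
- s, the chance that an affected participant volunteers the event: not in the documents, so assumed.
- p, the true share of participants affected: not in the documents, so assumed.

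**Step 3. What does a count of zero rule out?** With n people asked, all disclosing, the one-sided 95% upper bound after zero events is 1 − 0.05^(1/n).

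- n = 32: 1 − 0.05^(1/32) = 0.0894, or 8.9%.
- n = 26: 1 − 0.05^(1/26) = 0.109, or 10.9%.

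Under volunteered reporting, a participant is counted with probability p × s. The bound then applies to p × s, and the bound on p is 0.0894 / s.

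- s = 0.70: 0.0894 / 0.70 = 0.128, about 13%.
- s = 0.50: 0.0894 / 0.50 = 0.179, about 18%.
- s = 0.30: 0.0894 / 0.30 = 0.298, about 30%.

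**Step 4. How easily is a real event type missed?** The chance of seeing none is (1 − p × s)^32. For p = 10%:

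- s = 1: 0.90^32 = 0.034.
- s = 0.50: 0.95^32 = 0.194.
- s = 0.25: 0.975^32 = 0.445.

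**Step 5. What would a survey question add?** Volunteered reporting alone counts 32 × p × s participants on average. With a survey item answered by 80%, and volunteering still open to the rest, the expected count is 32 × p × (0.80 + 0.20 × s). This assumes that responders disclose fully and that responding is unrelated to having had an event.

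| Assumed p (truly affected) | s | Volunteered only | With survey item |
|---|---|---|---|
| 10% (3.2) | 25% / 50% / 75% | 0.8 / 1.6 / 2.4 | 2.7 / 2.9 / 3.0 |
| 30% (9.6) | 25% / 50% / 75% | 2.4 / 4.8 / 7.2 | 8.2 / 8.6 / 9.1 |
| 50% (16) | 25% / 50% / 75% | 4.0 / 8.0 / 12.0 | 13.6 / 14.4 / 15.2 |

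On these assumptions the survey item raises the captured share from 25–75% to 85–95%.

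**The case against.** The strongest reply is that silence is not absence. The opening commitment of section 4.2.3 stands apart from the contact arrangements, and nothing says those arrangements are the whole mechanism. Section 3.7 collects all remaining measures by online questionnaire, which leaves room for an adverse-event item. The list of measures is visibly incomplete: section 4.1 mentions questions on perceived stress and weight bias that appear in neither 3.6.1 nor 3.6.2. Section 4.2.5 points to fuller assessment protocols that are not reproduced. This stands. A question may exist undescribed, so the point is limited to what the documents describe.

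A reader might go further and infer three things that the documents do not support:

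- *That under-counting is certain, or that the promised coverage cannot be achieved.* No reporting rate is given, contact details recur weekly, and the channels are checked daily. Likely under-counting is as far as the text goes.
- *That participants have no visits or contact after randomization.* Section 3.3.2 speaks of remote evaluation visits and of follow-up by text, phone and email when assessments are overdue. What is missing is a described contact that asks about events.
- *That a planned comparison of events between easier and harder goals would be biased.* No such comparison is planned. Section 3.9 plans descriptive benchmarks and descriptive main effects on efficacy outcomes, and acceptability is measured by scheduled questions.

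It is also fair to say that setting volunteered reports against a perfect survey flatters the survey. That is why the bound for 26 responders is shown beside the one for 32. Finally, this is a small, 10-week behavioral pilot in screened adults with risks expected to be minimal. That limits the stakes but does not make volunteered counts interpretable.

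**Conclusion.** The point holds as a likely weakness in ascertainment. The promise covers all types of event, while the described post-randomization route depends wholly on participants coming forward, and the scheduled surveys are not described as asking. A low count would therefore be ambiguous between few events and few reports.

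The size is illustrative only. With every participant answering, zero events would exclude rates above 8.9%. With volunteered reports at 70% to 30% capture, it would exclude only rates above about 13% to 30%. The capture rates are assumptions, and the calculation treats participants as independent with the same chance of reporting. The sample size, the primary feasibility and acceptability outcomes, and the planned analyses are unaffected. The change is worth making, because it is cheap and the larger trial would inherit the method.

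**What to change.** Add a fixed adverse-event item to the 4-week and 10-week REDCap surveys for every participant, covering injury, soreness, health-care visit, hospitalization and distress since the last assessment. If such an item already exists, say so in sections 3.7 and 4.2.3. Keep spontaneous reporting as a second route between surveys, and report elicited and volunteered events separately, with the number who answered the item. A table by level of each goal (16 v 16 by design) is optional and should be descriptive only.

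The cost is one extra item at two existing time points, IRB approval of the wording (sections 3.7.4 and 4.2.5 already provide for amendments), and a longer list of minor events to record and, where required, report.
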